### **Pulmonary Vein Isolation (PVI)**

- Use point-by-point ablation to obtain a contiguous lesion set for ipsilateral PV isolation.
- Create VISITAG™ settings in order to segment the left atrium during the procedure according to below image (Figure 5).

**Figure 5: VISITAG™ settings**

- All subjects will undergo PV ablation with the investigational device until PVI is achieved in all targeted PV's:
  - ONLY after investigator deems unable to achieve PVI with the investigational device, a commercial and compatible BWI (RF) catheter and generator can be used to complete the procedure (PVI only).
- **REQUIRED:** Confirmation of entrance block (exit block is optional) / PVI of all clinically relevant targeted PVs
  - To verify entrance block, analyze electrograms in coronary sinus and/or atrial paced rhythm to confirm that no PV potentials are present.

### **Post Pulmonary Vein Isolation:**

- Administer adenosine/isoproterenol for each clinically relevant targeted PV to rule out dormant conduction.
  - If any, treat reconnected PV regions by reviewing remaining signals on reconnection location and deliver energy in corresponding locations.
- **REQUIRED:** Confirmation and documentation of final entrance block (exit block is optional) / PVI of all clinically relevant targeted PVs
  - To verify entrance block, analyze electrograms in coronary sinus and/or atrial paced rhythm to confirm that no PV potentials are present.

- Use a BWI multi-electrode mapping catheter for confirmation per investigators choice.
- The ablation procedure is considered complete when confirmation of entrance block in all clinically relevant targeted PVs is confirmed.
- **REQUIRED:** after last application or confirmation of final entrance block at the right sided PVs, evaluate diaphragmatic capture while pacing the phrenic nerve. NOTE: in case of deep sedation a fluoroscopic evaluation of the diaphragm might be used.
- A post paced activation and bipolar voltage map may be created at physician discretion and if SOC.
- **REQUIRED** for roll-in and PVI durability subset:
  - **REQUIRED:** creation of paced activation map and bipolar voltage map, using a BWI multi-electrode mapping catheter.
  - The OMNYPULSE™ Bi-Directional Catheter can be substituted (investigator discretion) prior to leave the LA.

### **Ablation outside the PV region**

- **A right atrial CTI linear** ablation is allowed only in cases with documented typical atrial flutter identified either prior to or during the procedure. The CTI line should be completed with a BWI commercially approved and compatible (RF) catheter and (RF) generator.
- **Prophylactic ablation** outside the PV region (in example SVC, PW, roofline) is NOT allowed.
- If an arrhythmia is requiring ablations outside the PV:
  - **Prior** to insertion of the study catheter (consistent with exclusion criteria) investigators will be required to switch to the commercial setup using a commercially available Biosense Webster catheter used with a commercially available RF generator. The subject will be considered a screen failure (<ICF signature) or excluded from the study (> ICF signature).
  - **After insertion of** the study catheter, the subject will undergo PVI with study set up followed by ablation with a commercially approved BWI (RF) catheter and compatible RF generator to complete the procedure for the treatment of arrhythmia outside PV region. The subject will be evaluable for acute success and followed till 3-months post procedure. NOTE: Ongoing AE(s) at 3 months shall be followed up until resolution (with or without sequelae)

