#### 4 Clinical Investigation Plan Summary

Full Title	Safety and Effectiveness Evaluation of the OMNYPULSE™ Catheter with the TRUPULSE™ Generator for treatment of Paroxysmal Atrial Fibrillation (PAF)
Short Title	Omny-IRE
CIP Number	BWI202201
Eudamed number	CIV-23-06-043176
Sponsor	Biosense Webster, Inc.
Description of Investigational Devices	
The Biosense Webster Pulsed Field (PF) Ablation System consists of the:
 
 
- TRUPULSE™ Generator (D-1417-01-IC)
 
- OMNYPULSE™ Bi-Directional Catheter (D-1430-05-SI)
 
- Sterile Interface Cable (D-1422-03-SI)
 
- Related components and accessories
 
 
CCI

Premarket or Post market	Premarket
Study Design	
Prospective, single arm, multi-center, pre-market clinical evaluation of the PF ablation system (OMNYPULSE™ Bi-Directional Catheter and TRUPULSE™ Generator) to demonstrate safety and effectiveness for the treatment of Paroxysmal Atrial Fibrillation (PAF) comparing to corresponding performance goals.
 
To minimize any learning curve effect, the first 2 study subjects treated by each ablating physician, will be considered roll-in subjects.
 
The main study will enroll 135 evaluable subjects with PAF who are candidates for atrial fibrillation ablation. Embedded within the main study will be a Neurological

	
Assessment (NA) subset, a Cardiac Computed Tomography (CT) or Magnetic Resonance Angiogram (MRA) image subset, an Esophageal Endoscopy (EE) subset and a Pulmonary Vein Isolation (PVI) durability subset in a prospective manner. These subsets are intended to delineate safety and assess lesion durability at 2-3 months following ablation. The same subjects will participate in all four (4) subsets.
 
All subjects will be followed for 12 months and scheduled for evaluation at 7 days, 1-, 3-, 6- and 12-month following index ablation procedure.

Study Population	Patients scheduled to have a clinically indicated ablation procedure for the management of their PAF.
Geographic areas to be included	Up to 14 sites in Europe and Canada.
Anticipated Study Timeline	
Estimated 20-22 months total study duration:
 
 
- Enrollment: Approximately 8-10 months
 
- Primary endpoint evaluation: 3 months post procedure
 
- Effectiveness evaluation: 12-months post procedure
 

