## **6.2 Additional Objective**

The additional objectives of this study are to evaluate procedural data, quality of life and the incidence of (procedure and/or device related) serious adverse events during and after procedure up to 12 months.

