## **7 Study design and Endpoints**

### **7.1 Description of the Study Design**

The study will be carried out as an interventional, prospective, multicenter, single-arm safety and effectiveness evaluation using the OMNYPULSE™ Bi-Directional Catheter in conjunction with the guiding sheath and the TRUPULSE™ Generator.

The study will enroll subjects with symptomatic PAF who are candidates for catheter ablation. Subjects who sign the Informed Consent Form (ICF) and who meet all eligibility criteria will be enrolled and treated with the OMNYPULSE™ Catheter and the TRUPULSE™ Generator.

The first two subjects for each ablating physician will be considered a roll-in subject to verify consistent workflow of study device components and to minimize any learning curve effects. The roll-in phase will include up to 50 subjects. A maximum sample size of 135 evaluable subjects is planned in the main study. All study subjects will be followed-up for 12 months after study procedure.

For the purpose of characterization of safety and to provide an assessment of lesion durability of the investigational ablation system, four (4) subsets will be embedded in the main study; the Neurological Assessment (NA), a Cardiac Computed Tomography (CT) or Magnetic Resonance Angiogram (MRA) imaging (CT/MRA), an Esophageal Endoscopy evaluation (EE) and a PVI durability subset in a prospective manner. Each subset will consist of the same 30 subjects, who will undergo the index ablation procedure and additional neurological, PV, esophageal and PVI durability assessments. The same subjects will participate in all four (4) subsets.

All subjects will be evaluated prior to the procedure, prior to discharge, and post procedure at 7 days (day 7-9), 1 month (day 23-37), 3 months (day 76-104), 6 months (day 166-194), and 12 months (day 335-379).

Planned statistical analyses of the endpoints and analysis populations are described in the Statistical Analysis section (section 19) of this clinical investigational plan and in the Statistical Analysis Plan (SAP). The results for the roll-in phase will be analyzed and presented separately from the main study phase.

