Stroke/Cerebrovascular Accident (CVA)	
Diagnosis:
 
 
-Rapid onset of a focal or global neurological deficit with at least one of the following: change in level of consciousness, hemiplegia, hemiparesis, numbness or sensory loss affecting one side of the body, dysphasia or aphasia, hemianopia, amaurosis fugax, or other neurological signs or symptoms consistent with stroke.
 
-Duration of a focal or global neurological deficit <math>\geq 24</math> h; or <math>< 24</math> h, if therapeutic intervention(s) were performed (e.g., thrombolytic therapy or intracranial angioplasty); OR available neuroimaging documents a new hemorrhage or infarct; or the neurological deficit results in death.
 
-No other readily identifiable non-stroke cause for the clinical presentation (e.g., brain tumor, trauma, infection, hypoglycemia, peripheral lesion, pharmacological influences).
 
-Confirmation of the diagnosis by at least one of the following: Neurology or neurosurgical specialist; Neuroimaging procedure (MR or CT scan or cerebral angiography); Lumbar puncture (i.e., spinal fluid analysis diagnostic of intracranial hemorrhage).
 
 
Definition: Stroke: (diagnosis as above, preferably with positive neuroimaging study)
 
 
Minor—Modified Rankin score <math>< 2</math> at 30 and 90 days
 
Major—Modified Rankin score <math>\geq 2</math> at 30 and 90 days
 

Transient Ischemic Attack	New focal neurological deficit with rapid symptom resolution (usually 1 to 2 h), always within 24h; neuroimaging without tissue injury.
Phrenic Nerve Paralysis (PNP)	Absent phrenic nerve function as assessed by a sniff test. Under this CIP, diaphragmatic paralysis/phrenic nerve palsy will be considered a Primary AE if specified symptoms have not improved and phrenic nerve function is confirmed to be absent by a sniff test at the 3-month visit. This reported PAE, is considered to be permanent when it is still documented to be present 12 months or longer following ablation.
Pulmonary Vein Stenosis 	A reduction of the diameter of a PV or PV branch. Severe PV stenosis ( $\geq 70\%$ reduction in the diameter of the PV) will be considered a PAE and major complication of AF ablation.

Primary Adverse Event	Description / Criteria

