### **19.8.3 Secondary Effectiveness Endpoint**

The secondary effectiveness endpoint of 12-month recurrence-free rate will be evaluated using the Kaplan-Meier estimate. The proportion for freedom from effectiveness failure events at 12-month, along with the two-sided 95% confidence interval, will be estimated. If the lower bound of the confidence interval is greater than the performance goal of 50%, the study will be considered to have demonstrated long-term effectiveness of the study system. Acute procedural failure (i.e., failure to confirm entrance block with or without touch-up in all PVs except those that are silent and/or cannot be cannulated post procedure) will also be deemed an effectiveness failure.

The 12-month effectiveness success analysis will be performed in the PP analysis set. However, per section 13.3 and 13.4, using a commercial RF device for the treatment of arrhythmia outside the PV region, such as for the ablation of a CTI line for documented typical AFL identified prior to or during the procedure, is allowed during index or within-blanking repeat ablation procedure. To filter out the potential effect of the commercial RF devices on the long-term effectiveness, these subjects will be censored at the time of using the commercial RF device for this 12-month effectiveness analysis.

If success is achieved in both the primary safety and acute effectiveness endpoints, then the secondary effectiveness endpoint will be tested. The secondary hypothesis test will be performed after all subjects have completed their 12-month follow up. The testing of the hypothesis for the secondary effectiveness endpoint after the success of the primary endpoints are met ensures family-wise error rate is controlled at a 2.5% level.

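### Subjects treated with the study device and then with RF outside the pulmonary veins are followed for only 3 months, against a 12-month rule for all subjects

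*Protocol*

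**What the plan says.** **The local rule.** Protocol 13.3.3, under *Ablation outside the PV region*, deals with an arrhythmia that needs ablation beyond the pulmonary veins. If this emerges after the study catheter is in, "the subject will undergo PVI with study set up followed by ablation with a commercially approved BWI (RF) catheter". The consequence is stated next: "The subject will be evaluable for acute success and followed till 3-months post procedure". A rider keeps events that are still open under observation: "NOTE: Ongoing AE(s) at 3 months shall be followed up until resolution (with or without sequelae").

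**The general rule.** The synopsis (Protocol 4) says "All subjects will be followed for 12 months and scheduled for evaluation". Protocol 7.1 says "All study subjects will be followed-up for 12 months after study procedure". Protocol 13.5 requires visits through 12 months, and SAP section 1 repeats 12 months for all subjects. None of these mentions an exception.

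**The disposition categories.** Protocol 19.5 gives 3-month follow-up to one category, discontinued subjects, defined by no energy having been delivered with the study catheter. SAP 7.2 uses the same categories.

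**What the later data are for.** Protocol 6.2 sets an objective covering "serious adverse events during and after procedure up to 12 months". Protocol 7.4.4 and SAP 7.11.2 report SAEs after Day 30 as late onset. Protocol 19.8.5 compares cardiovascular hospitalisation in the 12 months before and after the procedure.

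**The concern.** These subjects have had a full pulmonary vein isolation with the investigational system. For late safety they are as informative as any other treated subject, yet they get the follow-up length of subjects who received no study energy. They also fit none of the 3-month disposition categories, so the disposition table has no proper place for them.

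The effectiveness analysis does not need the early stop. Protocol 19.8.3 already deals with the influence of commercial RF by censoring in the 12-month effectiveness analysis. For a comparable case, a repeat procedure within blanking for non-PV triggers, Protocol 13.4 removes the subject from the long-term effectiveness cohort without shortening follow-up. No section gives a safety reason for stopping at 3 months.

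At stake are new SAEs, device effects and hospitalisations after 3 months in exposed subjects. The stop is triggered by what was ablated, so the missing observation is not a random sample.

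**Working it through.** The documents give no count of affected subjects and no figure for this point that could be reproduced. The check is therefore a comparison of passages, followed by day arithmetic.

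**1. Does any general section make room for the exception?** Protocol 4, 7.1 and 13.5 and SAP section 1 say 12 months without qualification. Protocol 19.5 shortens follow-up only where no study energy was delivered. The 13.3.3 group received study energy, so the conflict is not resolved elsewhere.

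**2. Observation lost per affected subject.** Inputs: stop at Day 90, planned end at Day 365, 3-month window Day 76 to 104 (Protocol 7.1).
- Stop at Day 90: 365 − 90 = 275 days; 275/365 = 75%.
- Stop at Day 76: 365 − 76 = 289 days; 289/365 = 79%.
- Stop at Day 104: 365 − 104 = 261 days; 261/365 = 72%.
- Share of the late-onset window (Day 31 to 365, 335 days): 275/335 = 82%.

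**3. Possible effect on the late-onset SAE percentage.** Assume a low, constant event hazard that is the same in affected and other subjects, and that affected subjects remain in the denominator. The relative understatement is then about (k/135) × (275/335), where k is the number affected.
- k = 1: 0.0074 × 0.821 = 0.6%.
- k = 4: 0.0296 × 0.821 = 2.4%.

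The range k = 1 to 4 (about 1% to 3% of 135) is an assumption for non-CTI targets only. If the true late SAE rate were 10% (also an assumption), the shift would be 0.06 to 0.24 percentage points.

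**4. Chance of missing an event.** Assume a 5% to 10% risk of a first SAE in Day 91 to 365. Expected subjects with a missed event: 1 × 0.05 = 0.05 up to 4 × 0.10 = 0.4. Probability of missing at least one: 1 − 0.95 = 5% up to 1 − 0.90⁴ = 34%.

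**5. Effect on the hypothesis tests.**
- *Acute effectiveness* is settled on the day of the procedure.
- *12-month effectiveness* censors these subjects at RF use, so later follow-up adds nothing to that test.
- *Primary safety* counts events to Day 90 at the latest (Protocol 7.4.1: related death, PV stenosis and atrio-esophageal fistula). A 3-month visit on Day 76 to 89 that closes follow-up leaves between 90 − 76 = 14 days and 90 − 89 = 1 day of that window unobserved. This is the only route to a primary endpoint.

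**The case against.** The best defence is that the rule is a deliberate local exception. These subjects would have met an exclusion criterion (Protocol 8.2, item 3) had the arrhythmia been known earlier. The all-subjects sentences already have one unlisted exception, the discontinued group, and three months covers the primary adverse event windows apart from an early visit. That shows the rule may be intended. It does not reconcile the sections or supply a reason to stop observing exposed subjects.

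Several stronger readings that a reader might infer are not supported:

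- **That every CTI-line case is cut at 3 months.** Protocol 19.8.3 does give RF outside the PV region an example, "such as for the ablation of a CTI line for documented typical AFL identified prior to or during the procedure". But 13.3.3 has a separate bullet permitting a CTI line for typical flutter identified before or during the procedure. The bullet with the 3-month rule also excludes subjects whose arrhythmia is found before catheter insertion. If it covered CTI flutter, the same subject would be both permitted and excluded. The non-CTI reading is the coherent one. Were CTI cases covered, an assumed 7 to 20 subjects would give 7/135 × 0.821 = 4.3% to 20/135 × 0.821 = 12.2%.
- **That the late SAE percentage is certainly biased.** SAP 7.11.2 states no denominator for the late window, SAP 7.1 and Protocol 19.4 base percentages on subjects with data, and the analysis-set definitions are redacted. The bias is possible, not established.
- **That permanent phrenic nerve paralysis cannot be classified.** Table 5 says it "is considered to be permanent when it is still documented to be present 12 months or longer following ablation". But it counts as a primary event only if still present at the 3-month visit. It is then an ongoing event, which the rider keeps under follow-up.
- **That no new event after 3 months can ever be recorded.** Protocol 14.4.1 requires AE reporting to the end of the study. However, Protocol 14.3 ties the enquiry about events to study visits, and these subjects would have none left. What is lost is systematic observation.
- **That hospitalisation is wholly compromised.** The 12-month Kaplan-Meier estimate in Protocol 19.8.5 accommodates shorter follow-up. Only the descriptive before/after comparison is exposed, because it would set 12 months against 3 for these subjects.

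**Conclusion.** The inconsistency is real and follows from the text alone. Subjects with full study-device exposure are released at 3 months, while four general statements promise 12 months and the only 3-month disposition category does not fit them.

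The consequence is limited. It falls on new late SAEs and device effects and on the before/after hospitalisation comparison, all descriptive. Each affected subject loses about 275 of 365 days. With 1 to 4 of 135 affected, the late SAE percentage could be low by about 0.6% to 2.4% in relative terms. That rests on the assumed count, a constant and equal hazard, and an unstated denominator. The primary and secondary tests are essentially unaffected, apart from the Day 76 to 89 gap in the primary safety window. The change is worth making because it is specific and inexpensive and concerns safety observation of exposed subjects, not because it threatens the trial's main conclusions.

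**What to change.** Reconcile Protocol 13.3.3 with Protocol 4, 7.1, 13.5 and 19.5 and SAP section 1:

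1. Continue safety follow-up (adverse events and hospitalisation) of these subjects through the scheduled 6- and 12-month visits. This also closes the Day 76 to 89 gap.
2. Keep the effectiveness censoring of Protocol 19.8.3 unchanged.
3. State that subjects with a permitted CTI line are not under the 3-month rule.
4. Give these subjects a disposition category in Protocol 19.5, and state the denominator for late-onset SAEs in SAP 7.11.2.
5. If any such subject has already left at 3 months, report the number and summarise late SAEs by person-time or Kaplan-Meier.

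The cost is a protocol modification, which may need competent authority and ethics committee approval under Protocol 10.2 if judged substantial, and two already scheduled visits for what is probably a few subjects. Subjects already past 3 months may need renewed consent.

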### **13.3.4 Collection of Ablation Procedure Data for Post-Analysis (non-SOC)**

At the completion of the study ablation procedure, two back-up copies of the CARTO™ and generator system log files will be made. One copy should be kept at the site within the investigator site or patient binders, and one fully anonymized copy will be provided to/collected by the Sponsor.

### **13.3.5 Data Collection during Study Ablation Procedure**

The following information will be collected during the procedure, including but not limited to:

**Technical parameters are collected via CARTO™ datafiles and TRUPULSE™ generator files, including but not limited to:**

- Number of PF applications.
- Energy delivered.
- PF application time.
- Ablation settings used.
- Contact force values.

**Other procedural parameters are collected via Electronic Data Capture (EDC), including but not limited to:**

- Use of a non-study catheter for PVI.
- Number of PF applications per left and right PV and by subject.
- Number of RF applications required with a non-study catheter.
- Use of a non-study multi-electrode catheter for mapping.
- PVI confirmed with BWI multi-electrode mapping catheter.
- PV acute reconnection.
- Procedure time (from first femoral puncture to last catheter out).
- Mapping time (start mapping – end mapping).
- Total fluoroscopy time.
- Total study catheter LA dwell time (from first study catheter insertion in LA until study catheter removal from LA).
- ECG data.
- Total fluid delivered via study catheter.
- Total fluid delivered via intravenous line (if captured).
- Fluid output (if captured).
- Device deficiency information (if applicable).
- Procedural medication (paralytics, ...).
- Use of paralytics and type of anesthesia.

### **13.3.6 Pre-Discharge Assessments**

Prior to hospital discharge, the following assessments should be performed:

- **Medication regimen** (Cardiac, anti-coagulation, PPIs)
- Imaging assessment of **pericardial fluid** presence
- **AEs**
- **12- Lead -ECG** (as per SOC)
- Additional Assessments for **NA subset** subjects (non-SOC): **Cerebral MRI, neurological exam and neurological evaluation using the NIH stroke scale** within 72-hours post procedure, preferable prior to discharge. A certified/qualified physician expert must perform neurologic exams at pre-and post-ablation and possibly at other follow-up visits, pending previous findings of micro-emboli/neurologic deficits. For procedures on Friday a window of maximum 96 hours is justified. Cerebral MRI images will be transmitted to an independent core laboratory. NOTE: Patient questionnaires will only be used in countries with validated languages.
- Additional assessments for **EE subset** subjects (non-SOC): **Endoscopy** to check for any esophageal lesions and/or damage will be performed preferable prior to discharge and no later than 72- hours after procedure (for procedures on Friday a window of a maximum of 96 hours is justified). Endoscopy images will be transmitted to an independent core laboratory.

